### **6.7. Visit 5 (Week 12, -7 days to +14 days)**

Visit 5 may be performed over 2 separate days if required. The following assessments will be performed:

- Perform concomitant medication review.
- Perform review of adverse events.
- Complete Child Behavior Checklist (CBCL).
- Complete Grooved Pegboard Test.
- Review bladder diary for completeness and check subject understanding of completion.
- Perform physical examination and weight measurement.

Measure vital signs (blood pressure, heart rate, temperature) after the subject has been in a sitting/resting position for at least 5 minutes.

- In subjects who are not performing intermittent catheterization, perform post-void residual (PVR) urine volume assessment using trans-abdominal ultrasound (eg, bladder scan) immediately after urination. PVR assessment is not required in subjects who empty their bladder using intermittent catheterization unless otherwise indicated (Section 7.2.6).
- Visual acuity and accommodation assessment.
- Clinical laboratory testing (approximately 5.5 ml of blood; see [Appendix 2](#)) including:
  - Hematology.
  - Blood chemistry.
  - Urine pregnancy test for all female subjects of childbearing potential.
  - Urinalysis and urine microscopy, culture and sensitivity if indicated.
- For subjects who had oxybutynin during the active comparator phase (Cohort 1, subjects >25 kg), pharmacogenomic blood sample taken (one sample, approximately 2 ml of blood; ([Appendix 2](#)) if the subject does not have prior laboratory documentation of CYP2D6 genotype and they are to continue in the safety extension).
- Perform urodynamic assessment including imaging of upper urinary tract if appropriate. Subjects who demonstrate a clinically relevant increased detrusor pressure compared to

baseline pressure or other urodynamic findings suggestive of worsening condition should not be allowed to continue into the safety extension phase.

- Review dosing log, and record details of time of last dose of fesoterodine or oxybutynin, and review electronic capture device.
- Collect appointment & dosing record card (for oxybutynin subjects only).
- Study medication return/count; assess compliance with study medication regimen.
- Dispense study medication.

#### **6.8. Visit 6 (Week 18, ±14 days)**

The following assessments will be performed at Visit 6 by telephone or clinic visit:

- Concomitant medication review;
- Review of adverse events;
- Review dosing log.

#### **6.9. Visit 7 (Week 24, -7 days to +14 days)**

The following assessments will be performed at Visit 7:

- Concomitant medication review.
- Review of adverse events.
- Complete Child Behavior Checklist (CBCL).
- Complete Grooved Pegboard Test.
- Perform physical examination and weight measurement.
- Measure vital signs (blood pressure, heart rate, temperature) after the subject has been in a sitting/resting position for at least 5 minutes.
- Visual acuity and accommodation assessment.
- Clinical laboratory testing (approximately 5.5 ml of blood; see [Appendix 2](#)) including:
  - Hematology.
  - Blood chemistry.

- Urine pregnancy test for all female subjects of childbearing potential.
- Urinalysis and urine microscopy, culture and sensitivity if indicated.
- In subjects who are not performing intermittent catheterization, perform post-void residual (PVR) urine volume assessment using trans-abdominal ultrasound (eg, bladder scan) immediately after urination. PVR assessment is not required in subjects who empty their bladder using intermittent catheterization unless otherwise indicated (Section 7.2.6).
- Review dosing log.
- Collect electronic data capture device.
- Study medication return/count; assess compliance with study medication regimen.

#### **6.10. Visit 8 (Follow-up, Week 26 +14 days)**

The following assessments will be performed at Visit 8 by telephone or clinic visit:

- Concomitant medication review;
- Review of adverse events.

Subjects who withdraw early from the study and who have taken at least 1 dose of study medication should be contacted by telephone approximately 2 weeks after stopping study medication.

#### **6.11. Additional Contacts**

Other contacts may also be made, as appropriate, to verify changes in dose, and to provide reminders to the subject to complete the bladder diary and daily dosing log. Contacts may take the form of telephone calls. Subjects should be contacted:

- At Week 1 to verify that they have correctly understood their dose regimen and if necessary to remind the subject to complete their daily dosing log. Subjects randomized to fesoterodine 8 mg, who have started at 4 mg should be reminded to start taking the 8 mg dose. Subjects randomized to fesoterodine 4 mg in Cohort 2 ( $\leq 25$  kg), who have started at 2 mg should be reminded to start taking the 4 mg dose.
- 1 week after Visit 5, to verify that subjects previously taking oxybutynin have correctly understood their dosing regimen, and a reminder for those allocated to the 8 mg dose that they need to change from the initial 4 mg to the 8 mg dose.
- Approximately 1 week prior to Visit 2 (unless the randomization visit occurs within 1 week of Screening (V1)) and prior to Visit 5, to remind the subject to complete the bladder diary and to review instructions on proper completion if needed. Subjects and/or

their caregivers should be re-educated and re-trained if review of data suggests that the bladder diary or dosing log are not being correctly completed.

## **6.12. Subject Withdrawal**

In France, see [Appendix 5](#).

If treatment is inadequate or the subject cannot tolerate the dose of fesoterodine or oxybutynin, consideration should be given to withdrawal.

Subjects who withdraw from the oxybutynin treatment arm (Cohort 1, >25 kg) for reasons of toleration, and who fulfill all continuation criteria, may be directly allocated by the investigator to fesoterodine treatment at either 4 mg or 8 mg/day for the remaining 12 week safety extension period if appropriate. All subsequent study visits should be scheduled relative to the start of the extension phase.

Subjects may withdraw from the study at any time at their own, or their legal representative(s) request, or they may be withdrawn at any time at the discretion of the investigator or sponsor for safety or behavioral reasons, or the inability of the subject to comply with the protocol required schedule of study visits or procedures at a given study site.

If a subject does not return for a scheduled visit, every effort should be made to contact the subject. In any circumstance, every effort should be made to document subject outcome, if possible. The investigator should inquire about the reason for withdrawal, request the subject to return all unused investigational product(s) and electronic diary equipment, request the subject to return for a final visit, if applicable, and follow-up with the subject regarding any unresolved adverse events (AEs).

Subjects in the fesoterodine groups who withdraw prior to Week 4 should have PK samples obtained as per Visit 3.

If a subject withdraws from the study prior to Visit 5 (Week 12), the same assessments as at Visit 5 should be performed if possible. Urodynamic assessment should only be performed in subjects who have been on a stable dose of study medication for at least 2 weeks, and who have not missed any doses in the 3 days prior to the visit.

If a subject withdraws from the study after Visit 5, the same assessments as at Visit 7 (Week 24) should be performed if possible.

Subjects who withdraw early from the study and who have taken at least 1 dose of study medication should also be contacted by telephone approximately 2 weeks after stopping study medication, and have the same assessments performed as at Visit 8 (Week 26).

If the subject withdraws from the study, and they or their legal representative(s) also withdraw consent for disclosure of future information, no further evaluations should be performed, and no additional data should be collected. The sponsor may retain and continue to use any data collected before such withdrawal of consent.

## 7. ASSESSMENTS

Every effort should be made to ensure that the protocol required tests and procedures are completed as described. However it is anticipated that from time to time there may be circumstances, outside of the control of the investigator, that may make the test unfeasible to perform. In these cases the investigator will take all steps necessary to ensure the safety and well being of the subject. When a protocol required test cannot be performed the investigator will document the reason for this and any corrective and preventive actions which they have taken to ensure that normal processes are adhered to as soon as possible. The study team will be informed of these incidents in a timely fashion.

### 7.1. Efficacy Assessments

#### 7.1.1. Urodynamic Assessments

Urodynamic assessment will be performed by persons qualified to perform pediatric urodynamics by education, training and experience, in accordance with International Children's Continence Society standards at Visit 2 (baseline) and Visit 5 (Week 12), (Neveus, et al, 2006). It should be performed with the subject awake, or if necessary under sedation, but general anesthesia is not permitted under this protocol. At Visit 2, previous treatment with prohibited concomitant medications must have a minimum washout appropriate to the drug so any clinical effect is at a minimum prior to baseline urodynamic evaluations eg, 3 day minimum washout for oxybutynin, 7 day minimum washout for darifenacin and solifenacin. At Visit 5 (Week 12), the time of the last dose of study medication (fesoterodine 2 mg, fesoterodine 4 mg, fesoterodine 8 mg or oxybutynin XL) prior to the urodynamic assessment should be recorded, and when possible urodynamic assessments should be completed approximately 4-6 hours post-dose. Typically a multichannel technique through a dual-lumen urodynamic catheter should be used. The bladder will be filled at a constant fill rate with test medium warmed to body temperature, until maximum cystometric capacity is reached as defined below, or in the judgement of the investigator, filling should be stopped.

Expected bladder capacity for age (mL) =  $[30 + (\text{child's age in years} \times 30)]$  mL up to the age of 12 years. From the age of 12 years onwards EBC is relatively constant at 390 ml.

The infusion rate should be based on 5% of expected bladder capacity per minute and will be recorded on the CRF.

The following will be evaluated:

- Maximum cystometric capacity, defined as maximal tolerable cystometric capacity, until voiding or leaking begins, or at a pressure of  $\geq 40$  cm H2O.
- Detrusor pressure at maximum bladder capacity.
- Maximum detrusor pressure.

- Presence of involuntary detrusor contractions (IDC).
- Bladder volume at first IDC, if present.
- Bladder wall compliance (ml/cm H2O), defined as  $\Delta\text{volume}/\Delta\text{pressure}$  during that change in bladder volume.
- Presence of subtraction test (eg cough) on urodynamic trace.

Where possible, both V2 and V5 urodynamic assessments for a subject should be performed by the same person. For all subjects, eligibility for study entry or continuation on the basis of urodynamic criteria will be verified by a central reader. Only the central reader's assessment of the urodynamic evaluation should be recorded in the CRF.

Prophylactic antimicrobial treatment may be administered at the discretion of the investigator and in line with local practice.

Attempts should be made to perform a urodynamic assessment in subjects who withdraw prior to Visit 5 (Week 12) and after a minimum of 2 weeks on a stable dose of study medication, provided that they have not missed any doses in the three days prior to the visit.

At Visit 5 (or end of active comparator/efficacy phase), subjects who demonstrate a clinically relevant increased detrusor pressure, or other urodynamic findings suggestive of worsening condition compared to baseline, should not be allowed to continue into the safety extension phase. In this case, consideration should be given to imaging of upper urinary tract (for example, videourodynamics or ultrasound) according to accepted local standard of care in subjects with VUR, or other conditions that predispose to upper urinary tract dysfunction or damage.

Full technical details are provided separately.

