## **2.2. Endpoints**

### **2.2.1. Primary Endpoint**

- Maximum cystometric bladder capacity defined as maximal tolerable cystometric capacity or until voiding/leaking begins or at 40 cm H2O.

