### **2.2.2. Secondary Endpoints**

#### **2.2.2.1. Efficacy Endpoints**

- Detrusor pressure at maximum bladder capacity.
- Presence of involuntary detrusor contractions (IDC).
- Bladder volume at first IDC.
- Bladder compliance.
- Mean number of micturitions and/or catheterizations/24 hrs.
- Mean number of incontinence episodes/24 hrs.
- Mean urgency episodes/24 hrs if applicable (only for sensate subjects).
- Mean volume voided per micturition or mean volume per catheterization.

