### **4.3. Continuation Criteria**

There must be no urodynamic evidence of clinically relevant increased detrusor pressure or other urodynamic findings suggestive of worsening condition compared to baseline, prior to continuation in the Safety Extension period.

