### **8.2.3. Secondary Analyses**

All secondary endpoints will be analysed as for the primary analyses as defined for each respective cohort using the appropriate full analysis set. A further analysis of the key secondary endpoints of Bladder compliance and IDC will use the per protocol analysis set.

The presence of IDC will be analyzed as for discrete endpoints.

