**8.2.6. Summary of Efficacy Endpoint Analyses**

| Endpoint  | Analysis Set    | Assessment | PLANNED Statistical Method   | Missing Data                | Interpretation                                    |
|---|-----------------|------------|--|-----------------------------|---|
| Change in maximum cystometric bladder capacity at week 12 relative to baseline                  | FAS (Cohort 1)  | Week 12    | ANCOVA – hypothesis testing approach; Descriptive statistics and subgroup summaries. | BOCF/LOCF (for ANCOVA only) | Primary analysis (for Cohort 1)                   |
|   | FAS (Cohort 2)  | Week 12    | ANCOVA – estimation approach; Descriptive statistics and subgroup summaries.         | BOCF/LOCF (for ANCOVA only) | Primary analysis (for Cohort 2)                   |
|   | PPAS (Cohort 1) | Week 12    | ANCOVA – hypothesis testing approach; Descriptive statistics.                        | No imputation               | Supportive to the primary analysis (for Cohort 1) |
|   | PPAS (Cohort 2) | Week 12    | ANCOVA – estimation approach; Descriptive statistics.                                | No imputation               | Supportive to the primary analysis (for Cohort 2) |
| Change in maximum detrusor pressure at maximum bladder capacity at week 12 relative to baseline | FAS (Cohort 1)  | Week 12    | ANCOVA – hypothesis testing approach; Descriptive statistics.                        | BOCF/LOCF (for ANCOVA only) | Secondary analysis (for Cohort 1)                 |
|   | FAS (Cohort 2)  | Week 12    | ANCOVA – estimation approach; Descriptive statistics.                                | BOCF/LOCF (for ANCOVA only) | Secondary analysis (for Cohort 2)                 |
| Presence of IDC   | FAS (Cohort 1)  | Week 12    | Categorical summaries  | BOCF/LOCF                   | Secondary analysis (for Cohort 1)                 |
|   | FAS (Cohort 2)  | Week 12    | Categorical summaries  | BOCF/LOCF                   | Secondary analysis (for Cohort 2)                 |
|   | PPAS (Cohort 1) | Week 12    | Categorical summaries  | No imputation               | Secondary analysis (for Cohort 1)                 |

| Endpoint  | Analysis Set    | Assessment | PLANNED Statistical Method                                    | Missing Data                | Interpretation                    |
|---|-----------------|------------|---|-----------------------------|-----------------------------------|

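### Detrusor pressure at capacity is read at a point partly set by the 40 cm H2O stop, so its change from baseline has no clear direction of benefit

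*Protocol*

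**What the plan says.** **Where the fill ends.** Protocol 2.2.1 has "Maximum cystometric bladder capacity defined as maximal tolerable cystometric capacity or until voiding/leaking begins or at 40 cm" H2O, and SAP 6.1.1 agrees. Protocol 7.1.1 has "Maximum cystometric capacity, defined as maximal tolerable cystometric capacity, until voiding or leaking begins, or at a pressure of" 40 cm H2O or more. The same section fills the bladder "until maximum cystometric capacity is reached as defined below, or in the judgement of the investigator, filling should be stopped", which adds investigator judgement as a further way for a fill to end.

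**What is read there.** Protocol 2.2.2.1 and SAP 6.1.2 both list the secondary endpoint "Detrusor pressure at maximum bladder capacity". Protocol 7.1.1 also lists "Maximum detrusor pressure" as a separate measurement. That second measure is in neither list of secondary endpoints.

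**How it is analysed.** SAP 8.2.3 says "All secondary endpoints will be analysed as for the primary analyses as defined for each respective cohort using the appropriate full analysis set". In SAP 8.2.6 the Cohort 1 row is an ANCOVA with hypothesis testing, labelled "Change in maximum detrusor pressure at maximum bladder capacity at week 12 relative to baseline". SAP 4.2 sets the level at 0.05 for changes from baseline in Cohort 1. Cohort 2 is estimation only.

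**Related rule.** Protocol 4.3 says "There must be no urodynamic evidence of clinically relevant increased detrusor pressure" before a subject enters the extension. Neither that section nor 7.1.1 says which pressure measure is meant.

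**What the supplied sections do not contain.** There is no analysis rule for fills ended by pressure and no pressure at a common volume. The reason for stopping is not among the items that 7.1.1 lists for evaluation. That section adds that technical details are held in a separate document.

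**The concern.** Pressure is one of the criteria that end the fill, and pressure at the end of the fill is then the outcome. Two things follow. A fill that ends on pressure at both visits gives roughly 40 cm H2O twice, so that child contributes about zero change. And when capacity changes, the two readings are taken at different volumes, so a bladder that holds more at lower pressure can still show a higher final reading.

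Protocol 1.2 names high bladder pressure as the route to upper-tract and renal damage, so a reader will look to this endpoint for evidence on that risk. Inclusion criterion 2 admits children on the basis of decreased compliance, so fills ended by pressure are foreseeable. A null or positive Cohort 1 estimate could be reported as no benefit or as harm when pressure at any given volume has fallen.

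**Working it through.** **The plan's own figure.** No power or standard deviation is stated for detrusor pressure. The nearest figure is the power for capacity in Protocol 9.1: 33 per group, change 70 mL, SD 120 mL, two-sided 5%. The noncentrality is 70 / (120/√33) = 3.35, and the t-test power is 0.901. The stated 90% reproduces, and nothing below alters it.

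**Model (assumed, for illustration).** Let C be compliance in mL/cm H2O, with linear filling, so P = V/C. Let L be the volume at which leak or tolerance would end the fill. Then

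- capacity V = min(L, 40 × C)
- pressure at capacity P = V/C = min(40, L/C).

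The second line gives the direction. P cannot move while both fills end at 40. It rises only if it was below 40 at baseline and L grows proportionally more than C. It falls if L grows proportionally less than C and the Week 12 fill ends before 40.

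**Single-child cases.** The common volume is the smaller of the two capacities. In each row that is the baseline capacity V0, so the Week 12 pressure there is V0 divided by the new C.

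| Fill ended by (baseline, Week 12) | C | L (mL) | Capacity (mL) | Pressure at capacity | Change | Pressure at common volume |
|---|---|---|---|---|---|---|
| pressure, pressure | 4 to 6 | 300 to 400 | 160 to 240 | 40 to 40 | 0 | 40 to 160/6 = 26.7 |
| leak, pressure | 4 to 6 | 120 to 260 | 120 to 240 | 30 to 40 | +10 | 30 to 120/6 = 20 |
| leak, leak | 4 to 6 | 120 to 150 | 120 to 150 | 30 to 25 | -5 | 30 to 120/6 = 20 |
| pressure, tolerance | 4 to 8 | 300 to 300 | 160 to 300 | 40 to 37.5 | -2.5 | 40 to 160/8 = 20 |

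Every child improves in compliance and capacity. Pressure at capacity shows no change, a rise or a fall. Pressure at the common volume falls in all four.

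**Populations.** Assumed: 200,000 children per scenario; compliance lognormal with median 6 and log-SD 0.6, rising 50% in everyone; L lognormal with median 100, 150, 200 or 300 mL and log-SD 0.5.

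| Rise in L | Mean change in capacity (mL) | Mean change in pressure at capacity (cm H2O) |
|---|---|---|
| none | +5 to +47 | -5.9 to -4.7 |
| 25% | +30 to +82 | -2.7 to -1.9 |
| 50% | +53 to +108 | about 0 |
| 75% | +74 to +129 | +1.4 to +2.2 |

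Ranges run over the four medians. Capacity falls in no child, so the common volume is V0 and pressure there falls from V0/C to V0/(1.5C), a one-third drop in every child in every scenario. The sign of the mean change at capacity therefore depends on how far L moves relative to C, not on whether the bladder improved. The share of fills ended by pressure at baseline was 13% to 61% across these assumptions; the documents give no figure.

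**The case against.** The strongest reply is that the plan already measures this benefit. Bladder compliance is a separate secondary endpoint, SAP 8.2.3 calls it key, and it is analysed in both the full and per-protocol sets. Under the linear model, pressure at a fixed volume is a function of compliance. Larger capacity also registers in the primary endpoint. This stands in part: a real benefit would not vanish from the report. But the volume interval for compliance is not specified, and a good compliance result does not tell the reader how to interpret the separately reported pressure test.

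Four stronger readings are tempting, and the documents do not support them.

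- *The endpoint is fixed at 40 cm H2O.* Only fills ended by pressure are constrained. Tolerance, voiding or leaking, and investigator judgement also end fills, and pressure is then free to fall. With a stop written as 40 or more, a reading can also exceed 40.
- *The SAP replaced the endpoint with maximum detrusor pressure.* SAP 6.1.2 keeps the protocol name. The 8.2.6 row adds one word and retains the reference to capacity. It may be a slip, though it blurs two measures that Protocol 7.1.1 lists apart.
- *Improved children will be barred from the extension.* Protocol 4.3 and 7.1.1 do not tie the continuation criterion to pressure at capacity, and a central reader verifies it.
- *The reason for stopping is not recorded.* It may be covered in the separate technical document, so its absence cannot be asserted.

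An average rise should not be predicted either. In the model it needs leak or tolerance volume to grow proportionally more than compliance.

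**Conclusion.** The point holds in a limited form. Detrusor pressure at capacity is partly constrained by the stop that helps define capacity, and its two readings are taken at different volumes whenever capacity changes. For fills ended by pressure at both visits the change is about zero whatever the benefit. A move from an early leak to the pressure stop appears as a rise. The Cohort 1 test of this change against zero therefore has no clear direction of benefit.

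The existence of the problem follows from the definitions. Its size does not: the -5.9 to +2.2 cm H2O range rests on linear filling, a uniform 50% compliance gain and assumed distributions, and it is not a forecast for this trial. The endpoint is secondary, and the primary endpoint, sample size and power are untouched. The change below is a cheap improvement in interpretability.

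**What to change.** 1. Keep the protocol endpoint and its planned analysis.
2. Add to the SAP a supportive ANCOVA of detrusor pressure at a common volume, defined as the smaller of the subject's Visit 2 and Visit 5 capacities. The central reader already in place would read it from the same traces.
3. Tabulate the change in pressure at capacity by which criterion ended the fill at each visit. If the reason was not captured, split at minimum by pressure at capacity of 40 cm H2O or more versus below, which uses data already collected. Apply the split alike to rises and falls.
4. Change the SAP 8.2.6 row label to the name in SAP 6.1.2 and Protocol 2.2.2.1.
5. Reconcile the stop pressure, which is at 40 in Protocol 2.2.1 and SAP 6.1.1 but 40 or more in Protocol 7.1.1. Also reconcile Protocol 4.3 and 7.1.1 on which detrusor pressure the continuation criterion means. No clinical rule is proposed here.

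Cost: SAP wording, one table and one extra value read per existing trace. No new procedure, visit or change in sample size.
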